#### 5.6.1 Dose Titration Period (up to 9 Weeks)

There will be a total of approximately 60 patients randomized to either active treatment or placebo in a 2:1 ratio. The starting dose is 0.01 mg APD811 twice daily (b.i.d.) or placebo. Thus, the identity of study drug (active or placebo) will be blinded, but the dose level is not. Patients will be observed for at least 4 hours after the initial dose of APD811 and after each subsequent dose escalation. A pre-dose and a 4-hour post-dose PK sample will be collected at each study visit in which dose escalation is planned. Adverse events, blood pressure, and heart rate will be monitored during the observation period. The observation period may be extended based on the judgment of the investigator. If deemed necessary by the investigator, the patient may be monitored as an in-patient for the initial dose and/or subsequent increases in dose. The medical monitor should be notified in any instance that prolonged observation and/or in-patient monitoring is anticipated or required.

If a dose is not tolerated, the study drug may be decreased to the previous dose level. If the initial dose of 0.01 mg b.i.d. is not tolerated, dosing may be decreased to 0.01 mg q.d.

If the initial dose is tolerated (0.01 mg b.i.d.), the dose will be increased in the following fashion at subsequent visits: 0.02 mg b.i.d., 0.03 mg b.i.d., 0.04 mg b.i.d., 0.06 mg b.i.d., 0.08 mg b.i.d., 0.1 mg b.i.d., 0.2 mg b.i.d and 0.3 mg b.i.d. The dose may be escalated to a maximum total daily dose of 0.6 mg (0.3 mg b.i.d.) depending on tolerability.

Prolonged dosing may result in tolerance to some adverse effects and thus, more than 1 week between dose escalations may be required. However, Investigators are encouraged to dose escalate to the highest possible dose within the 9-week dose titration period. If a particular dose is not tolerated, treatment may be reduced to a previous dose as directed by the investigator. The dose may be decreased for safety reasons at any time, but may not be increased without assessment in the clinic.

Table 3 indicates the dosing regimen during the 9-week dose titration period. This dosing regimen (starting dose, dose increments, dosage forms, duration) may be modified during the course of the study by the Safety Monitoring Committee based on cumulative patient experience. In order to simplify dose titration, the 0.01 mg dose strength will be used during the initial portion of the dose titration.

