1.2 Description of the Study and Objectives/Hypotheses

1.2.1 Summary of Study Design

APD811-003 is a 22 week, randomized, double-blind, placebo controlled study which includes a dose titration period of up to 9 weeks. An additional transition period of 3 weeks (± 1 week) will occur for those patients who elect to enroll into the open-label extension study, APD811 007. Patients that do not continue in the extension study will have a 3 week follow-up visit. Patients will be randomized 2:1 active to placebo. Approximately 60 patients with PAH will be enrolled. At the end of the treatment period, all patients that choose to continue in the open-label extension study (OLE: APD811-007) will remain on study treatment until the follow-up visit at Week 25. This visit will serve as the baseline visit for the open-label extension study if the patient is eligible and chooses to participate (see Appendix 1). Patients who do not choose to participate in the OLE will discontinue treatment at the end of the treatment period.

Safety will be assessed by the Safety Monitoring Committee (SMC) as documented in the SMC Charter. The SMC will review safety data including adverse events, blood pressure and heart rate periodically during the dose titration period and the treatment period, in order to ensure patient safety and determine an appropriate dose titration regimen.

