For the time to first event of clinical worsening endpoint, the duration is defined as from randomization to first occurrence of clinical worsening, otherwise it will be censored at the last recorded date of clinical worsening event assessment or end of study, whichever is later. The cumulative event rates and graphic presentation will be estimated and produced using the Kaplan-Meier method. Non-parametric methods such as the log-rank test stratified by baseline WHO/NYHA functional class stratum will be utilized to compare the survival curve by treatment group. A Cox proportional hazards model will be applied to compare the hazard rates between treatment groups. The model will include treatment, baseline PVR and WHO/NYHA stratum as factors. The hazard ratio (HR) between the treatment groups (APD811 /placebo) will be estimated. The 95% CIs around the estimated HR along with event rates per 100 person years will be presented. Analytical and graphical methods will be employed to verify the proportional hazard assumption. The proportional hazards assumption will be tested by including the factor $\text{treatment} * \log(\text{time})$ in the model; nonsignificance ($p > 0.05$) of this factor implies proportionality, i.e., constancy of treatment effect over time.

Other exploratory analyses may be performed to further assess treatment effects on efficacy measures, and relationships between during treatment measures. There will be no inferential testing for these analyses and only point estimate and corresponding confidence interval will be reported. Analyses related to baseline subgroup will be described in section 6.2. Followings are potential exploratory analyses.

- Relationships between study drug exposure (intensity and duration) and efficacy measures (PVR, 6MWD, WHO/NYHA FC, BNP/NT-proBNP, etc.)
- Correlations between Week 22 efficacy measures (PVR vs. 6MWD, PVR vs. WHO/NYHA FC, 6MWD vs. WHO/NYHA FC, BNP/NT-proBNP vs. PVR, BNP/NT-proBNP vs. 6MWD, etc.)
- Proportion of patients achieving $\geq 10\%$ 6MWD increase from baseline at Week 22
- Proportion of patients achieving ≥ 440 meters 6MWD at Week 22
- Proportion of patients achieving clinical improvement at Week 22, such as $\geq 10\%$ 6MWD increase from baseline and WHO/NYHA FC I or II
- Proportion of patients achieving normalized PVR (< 240 units) at Week 22
- Proportion of patients achieving $\geq 15\%$ in PVR reduction from baseline at Week 22

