7 STATISTICAL TECHNICAL ISSUES

7.1 Planned Statistical Power and Sample Size

For the APD811 versus placebo comparison, 28 patients in the APD811 group and 14 patients in the placebo group will have 90% power to detect a between-treatment difference of 350 dyn·s·cm⁻⁵ in PVR. This calculation was based upon the pooled SD estimate of 320.3 dyn·s·cm⁻⁵ for the mean change from baseline in PVR at Week 17 observed in the selexipag phase 2 study.

Assuming that up to 30% of patients may drop out of the trial before a post-randomization repeat RHC is performed, 40 patients will be randomized to the APD811 group and 20 patients will be randomized to the placebo group. For 6MWD, 40 patients in APD811 group and 20 patients in the placebo group will have 80% power to detect a between-treatment difference of 50 meters in 6MWD assuming pooled SD estimate of 65 meters.

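### SAP 4.3.3 reads a non-significant treatment by log(time) term as proof of proportional hazards, an invalid rule resting on a test with low power in this trial

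*SAP*

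**What the plan says.** Time to first clinical worsening is an exploratory endpoint (SAP 4.1). Under SAP 4.3.3 its clock starts at randomization: "the duration is defined as from randomization to first occurrence of clinical worsening". The section plans Kaplan-Meier estimates and curves, a stratified log-rank test and a Cox model. Of the Cox model it says: "The model will include treatment, baseline PVR and WHO/NYHA stratum as factors".

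On proportional hazards it makes three statements in sequence:

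- A general one: "Analytical and graphical methods will be employed to verify the proportional hazard assumption".
- A specific test: "The proportional hazards assumption will be tested by including the factor" treatment*log(time).
- A rule for reading that test: non-significance, with p above 0.05, "of this factor implies proportionality, i.e., constancy of treatment effect over time".

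It gives no expected event count, no power for the test, no estimate or interval for the interaction, and no wording for a term that cannot be estimated.

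On size, SAP 7.1 says "40 patients will be randomized to the APD811 group and 20 patients will be randomized to the placebo group". On timing, SAP 1.2.1 describes a 22-week study "which includes a dose titration period of up to 9 weeks". Protocol 5.6.1 says investigators are "encouraged to dose escalate to the highest possible dose within the 9-week dose titration period".

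**The concern.** A p-value above 0.05 says that the data do not contradict a constant hazard ratio at that threshold. It does not say that they support one. The rule treats the two as the same, which is an error at any sample size and needs no assumption about event rates.

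The error has some practical weight here because few events are likely among 60 patients followed for 22 weeks. Up to 9 of those weeks are titration, and they lie inside the risk period. A treatment effect that differs between the early and later weeks is therefore plausible, although neither document says so. At stake is whether one exploratory hazard ratio is read as constant over all 22 weeks on the strength of a test that could rarely have shown otherwise.

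**Working it through.** **Inputs from the documents.** 40 APD811 and 20 placebo patients, and drop-out of up to 30% (SAP 7.1); 22 weeks with up to 9 of titration (SAP 1.2.1); start of the clock and form of the test (SAP 4.3.3).

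**Inputs assumed.** No clinical-worsening rate is given. The only event figure is annual mortality of about 15% (Protocol 1.1.1), which is a different endpoint. Placebo 22-week risk was therefore varied over 10%, 15%, 25%, 40% and 60%. The hazard-ratio patterns, changing at Week 9, are also assumptions.

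**The plan's own figures.** These reproduce.

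- PVR: 350 / (320.3 × √(1/28 + 1/14)) = 3.34. Normal-approximation power is Φ(3.34 − 1.96) = 91.6%; noncentral t gives 90.3%, against 90% stated.
- Drop-out: 28/0.7 = 40 and 14/0.7 = 20.
- 6MWD: 50 / (65 × √(1/40 + 1/20)) = 2.81, giving 80.2% (78.9% by t), against 80% stated.

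There is no stated figure to reproduce for the proportional-hazards test.

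**Events needed, rough formula.** For a ratio r of late to early hazard ratio, 80% power needs about

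events = (1.96 + 0.8416)² / [w(1 − w) × (2/9) × (ln r)²], with w = 9/22.

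Here w(1 − w) × 2/9 = 0.0537 and the numerator is 7.849.

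- r = 0.5: 7.849 / (0.0537 × 0.480) gives 305 events.
- r = 0.3: 7.849 / (0.0537 × 1.450) gives 101 events.
- r = 0.1: 7.849 / (0.0537 × 5.302) gives 28 events.

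At most 60 first events are possible. The formula is optimistic, because a strong late effect removes the late active-arm events that the test needs.

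**Simulation.** 1,500 trials per cell, with placebo hazard −ln(1 − risk)/22 per week. The Cox model has treatment and treatment*log(time), with a Wald test at two-sided 0.05. Non-estimable fits count as not rejected. Baseline PVR and functional class are omitted. Rejection rates without drop-out:

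| Placebo risk | Mean events (HR 1→0.3) | HR constant at 1 | 1→0.5 | 1→0.3 | 1→0.1 | 2→0.3 |
|---|---|---|---|---|---|---|
| 10% | 4.4 | 0.2% | 0.0% | 0.0% | 0.0% | 0.0% |
| 15% | 6.6 | 0.1% | 0.1% | 0.1% | 0.0% | 0.5% |
| 25% | 11.2 | 0.5% | 0.4% | 0.7% | 0.9% | 4.0% |
| 40% | 18.3 | 1.2% | 3.9% | 6.5% | 11.3% | 16.8% |
| 60% | 28.4 | 3.5% | 7.2% | 15.1% | 26.8% | 27.5% |

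With 30% drop-out, the highest power is 12.5% at risks up to 40%, and 21.8% at 60%. Simulation error near 17% is about √(0.17 × 0.83 / 1500) = 1 percentage point.

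**What p > 0.05 is worth as evidence.** At 40% risk a non-significant result occurs in 98.8% of trials with a constant hazard ratio and in 83.2% with HR 2→0.3, the most detectable pattern. The ratio is 98.8/83.2 = 1.19. At 60% it is 96.5/72.5 = 1.33. A result that shifts the odds so little cannot imply constancy.

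**Likelihood-ratio version.** The SAP does not say which test applies. At 10–40% risk this version rejects in 12–33% of trials when the hazard ratio changes. Its type I error under a constant hazard ratio is 16.7%, 12.1%, 8.3%, 5.6% and 5.7% at the five risks, so at the lower risks many rejections are false. At 40% risk, where its size is near nominal, power is still only 11.5–32.8%.

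**Estimability.** Counting only trials with fewer than three events or with all events in one arm, 4–10% of fits fail at 15% risk without drop-out when the hazard ratio changes. The share is larger when one also counts trials in which all events in one arm precede all those in the other, because the estimate is then infinite. With large Week 9 changes and 20–30% drop-out it is then about 30–45% at 15% risk. For HR 1→0.2 with 20% drop-out it is about 11% at 25% risk and 1% at 40%.

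**The case against.** The strongest reply is that little depends on this sentence, and much of that stands.

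- The test is not the only check. The general sentence just before it plans analytical and graphical methods, and plots might show a pattern that the test misses. They have no stated criterion, however, and with few events they cannot establish constancy either.
- A between-arm comparison that does not need proportional hazards already exists. SAP 4.3.2 gives the difference in the proportion worsening with a 95% CI, at secondary level. SAP 7.4 adds a version that counts every premature discontinuation as an event, and SAP 4.3.3 gives Kaplan-Meier rates. The crude proportion does not account for censoring, so a small gap remains.
- No analysis branches on the test. The hazard ratio, its CI, the log-rank test and the curves are reported whatever it shows. A reader might infer that the report must assert a constant hazard ratio, but the SAP prescribes no such statement.
- A reader might also infer that the design makes a changing effect the expected pattern. The documents do not support that. A 30-fold increase (0.3/0.01) is the ceiling of individual titration, and Protocol 5.6.1 provides for patients who reach their highest tolerated dose before Week 9. Protocol 1.1.1 places receptor pharmacology from 0.01 mg upwards in healthy volunteers. A changing effect is plausible, and no more than that.

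None of this makes the stated inference valid.

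**Conclusion.** Wrong as written, with a small consequence. The logical error is certain. The size of the power problem is conditional: about 0–17% for the Wald test at assumed placebo risks of 10–40% and below 30% at 60%, for large Week 9 changes in a model without the planned covariates.

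Two stronger statements should not be made. Almost no power is a fair description only of the Wald test at the lower assumed event rates. And a figure of 93–99% of trials declaring proportionality (HR 1.0 then 0.2, 20% drop-out, risks of 15–40%) counts non-estimable fits as non-significant, so at the low end part of it is model failure and not a valid p-value above 0.05.

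No primary or secondary conclusion is touched. Only the interpretation of the exploratory hazard ratio changes, so this is a desirable correction and not an essential one.

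**What to change.** In SAP 4.3.3:

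- Delete the clause that reads p above 0.05 as proportionality and a constant effect.
- Report the treatment*log(time) estimate with its 95% CI beside the planned plots.
- Describe a non-significant or non-estimable result as inconclusive.
- Describe the Cox hazard ratio as an average over the follow-up period.

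Optionally, add the Week 22 Kaplan-Meier risk difference with a 95% CI. It handles censoring and complements the crude difference already planned in SAP 4.3.2.

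The cost is a wording change and one or two output lines from models already planned. No new data are needed and the primary analysis is unaffected.

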4.4 Pharmacokinetic Analysis

APD811 plasma concentrations are limited to pre-dose (C_{\min}) and 4 hours post-dose. APD811 plasma steady-state will be determined by regressing C_{\min} values over time and the resultant slope tested for its difference from zero. Individual APD811 plasma concentrations at specified time points will be listed for each patient by treatment group. Individual plasma concentration-

time points of APD811 will be plotted on both a linear and a semi-logarithmic scale for each dose level.

4.5 Definition of Compliance Measure

Compliance will be assessed using patient data recorded in the drug accountability form of the electronic case report forms (eCRFs). On each day, a patient should take his/her assigned treatment. The compliance rate for each patient will be computed as $100\% \times (\text{the total dose received} / \text{the total dose planned})$. Days on treatment is defined as the number of days from the date of first dose to the date of last dose. Compliance rates will be summarized for each treatment arm.

5 SAFETY ANALYSES

Safety and tolerability will be assessed by a review of all safety parameters including adverse experiences (AEs), laboratory safety parameters, vital signs, and ECG. Only summary tabulations (N, mean [or median], SD, mean [or median] change/percent change). The 95% CIs for between-group differences will be reported for special safety analysis. Adverse experiences will only be presented as summary tabulations.

5.1 Safety Population

The analyses for all safety outcomes (categorical or continuous measures) will use the safety population which consists of all randomized patients who received at least 1 dose of study drug; in addition, if a patient is found to have taken a study therapy for the entire duration of the study different from that to which he/she was randomized, then the patient is counted in the treatment group of the drug he/she actually received.

For analysis based on laboratory measurements, at least 1 laboratory test post-randomization is required for inclusion in the safety population. When assessing change from baseline, a baseline measurement is also required. Baseline for the safety analysis is defined as the last pre-randomization measurement. -

5.2 Dose, Duration, and Dose Modification

The number and percentage of patients will be summarized based on the final dose level (the last treatment dose). 0.2 mg b.i.d. or 0.3 mg b.i.d. is the achieved target dose in this study. The number and percentage of patients whose final dose reached the achieved target dose will be summarized as well. The duration of treatment for each patient will be assessed by calculating the number of days on drug from the date of the first dose to the date of the last dose. For each arm, the range (minimum and maximum) of values for days on drug and the mean number of days on drug will be calculated.

Additionally, the number and percentage of patient with at least one missed/interrupted dose and at least one dose reduction will be summarized separately. The missed/interrupted dose is defined as either Total Daily Dose is "0" or there is gap between the last date of previous treatment record and the first date of the next treatment record. The total days of the gap and the "0" daily dose will be considered as days of missed/interrupted dose of the patient. The number and percentage of patients with the different missed/interrupted dose and the different maximum dose before dose reduction will be summarized.

These summaries will be based on safety population, completers population and patients with early treatment discontinuation.

5.3 Adverse Events

Adverse events will be coded using the most current Medical Dictionary for Drug Regulatory Affairs (MedDRA) and tabulated, including categorical information of interest such as onset and resolution times, time of onset relative to dose, severity at onset, maximum severity, causal

relationship to study medication, and action taken. AEs will be regarded as ‘pre-treatment’ if they occur between screening and the time of administration of the first dose of APD811 or placebo and will be recorded as medical history. All other AEs that occur or worsen after the first dose of study medication will be considered to be ‘treatment-emergent’. Missing or incomplete start date of AE will be imputed as section 7.4.

Treatment-emergent AEs (TEAE) will be listed by patient and by treatment. They will be summarized per treatment and expressed in terms of maximum severity and relationship to study medication. The incidence of TEAEs classified according to system organ class will be summarized by treatment group. TEAEs will also be summarized by maximum intensity (assessed according to the Common Terminology Criteria for Adverse Events v4.03² definitions) and relatedness to study medication.

Summaries of the number (%) of patients in each treatment group with at least 1 TEAE, classified according to MedDRA system organ class and preferred term, will also be provided for:

- Drug-related TEAE
- Treatment-emergent AEs leading to permanent discontinuation of study medication (study medication discontinued or withdrawal from study).
- Serious adverse events (SAEs)
- Prevalence of selected treatment-emergent AEs over dose titration and treatment periods

Serious adverse events will be listed by patient and by treatment. If there are no SAEs at the end of the study, the tables or listings will state that there are no SAEs in the study.

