Study drug administration v		X	X	X	X	X	X	X	X	X	X
Pharmacokinetic blood sample w		X	X	X	X	X	X	X	X	X	X
Adverse event monitoring	•	-	•	-	•	•	•	-	•	•	→
Concomitant medication monitoring	←										→

Optional blood sample (4mL) for DNA testing, to be taken pre-dose on Day 1.

<sup>m Serum hCG pregnancy test required at Screening and at Week 5; urine pregnancy test at Day1.

<sup>n Blood sample for BNP/NT-proBNP to be taken after 1-hour rest and prior to administration of 6MWT.

<sup>o 6MWT should be completed pre-dose at approximately the same time of day at each designated visit.

Two 6MWTs are required during Screening and each test must be performed on a separate day. The distance walked during each test must be ≥100 meters and ≤500 meters, and within 15% of each other in order to be eligible for the study.

Thromboembolic disease assessment to include a V/Q scan or spiral/helical/electron beam computed tomography utilizing an angiography protocol, or selective pulmonary angiogram, unless performed within 5 years prior to Screening.

Pulmonary function test (PFT) to be completed at screening. A PFT completed within 6 months prior to Screening may be acceptable (see inclusion criteria #9).

s See exclusion criteria #10

t Transthoracic or transesophageal ECHO, unless performed within 12 months prior to Screening.

<sup>u A Baseline RHC is required. Patients who have had a RHC performed within 30 days of screening and meet study entry requirements are not required to have a repeat screening RHC.

V Should be taken with food.

Blood samples for PK will be collected at pre-dose and at 4 hours post-dose during every visit in which dose escalation occurs and one week after the last dose escalation. An additional blood sample for PK analysis will be collected if possible at the time of any intolerable AE or SAE.

Table 2. Schedule of Procedures and Visits: Treatment and Dose Transition Periods

			Transition Period				
Evaluation a		Treatment Period	End of Study (EOS) Visit	Follow-up Visit (start of OLE) ±1 week b			
Study Week	10	14	18	22°	25		
Day	70	98	126	154	175		
Physical exam				X	X		
Safety ECG (12-lead) d	X	X	X	X	X		
Clinical laboratory tests e	X	X	X	X	X		
Serum pregnancy test f	X	X	X	X	X		
Vital signs g	X	X	X	X	X		

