## 6.13.1 Adverse Event Reporting

Patients will be instructed that they may report AEs at any time. AEs will be regarded as 'pre-treatment' if they occur between Screening and the time of administration of the first dose of APD811. All events reported following study medication administration will be recorded as treatment emergent AEs (TEAE).

Monitoring of AEs will be continued **up to 30 days** after study medication administration. In the event that an AE is not resolved or stabilized by this time, the sponsor in consultation with the investigator will decide whether to continue to monitor the AE or close-out the event in the database if no further follow-up is necessary.

For this study, an AE is defined as: "Any untoward medical occurrence in a study patient administered any dose of study medication (APD811 or placebo) and which does not necessarily have to have a causal relationship with this treatment." An AE can therefore be any unfavorable and unintended sign (including an abnormal laboratory finding), symptom, or disease temporally associated with the use of the study medication, whether or not related to the product. Worsening of underlying disease (section 6.9) will not be considered to be an adverse event.

AEs can be any of the following:

- Unfavorable changes in general condition
- Subjective or objective signs/symptoms
- Concomitant disease or accidents
- Clinically relevant adverse changes in laboratory parameters observed in a patient in the course of a clinical study

 Pre-existing conditions which worsen in severity or frequency or which have new signs/symptoms associated with them

Adverse events will be elicited at the time indicated in the schedule by asking the question: "Since you were last asked, have you felt unwell or different from usual in any way?" Any adverse or unexpected events, signs and symptoms, will be fully recorded on the Adverse Event Form including details of intensity, onset, duration, outcome and relationship to the drug as determined by the PI. Whenever possible, a constellation of signs and symptoms should be recorded as a unifying diagnosis (e.g., self-limited fever, runny nose, cough, and scratchy throat should be captured as an upper respiratory infection rather than by the individual signs and symptoms). AEs may also be reported at any time. The type and duration of follow-up of patients after AEs will be documented.

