# 6.13.2 Serious Adverse Events and Expedited Reporting of Adverse Events

A Serious Adverse Event (SAE) is any untoward medical occurrence that at any dose results in the following outcomes:

- Death
- Is Life-Threatening
- Required/Prolonged Hospitalization
- Disability/Incapacity
- Congenital Anomaly/Birth Defect
- Important Medical Event

SAEs will be captured from the time of screening to 30 days after the dose of study drug, and will be monitored until resolution or stabilization.

An important medical event that may not result in death, be life-threatening, or require hospitalization may be considered a SAE when, based upon appropriate medical judgment, it may jeopardize the patient and may require medical or surgical intervention to prevent one of the outcomes listed in this definition. Examples of such a medical event includes allergic bronchospasm requiring intensive treatment in an emergency room or at home, blood dyscrasias, or convulsions that do not result in in-patient hospitalization, or the development of drug dependency or drug abuse.

Elective hospitalization and/or surgery for clearly pre-existing conditions (for example a surgery that has been scheduled prior to the patient's entry into the study) will not be reported as a SAE. All other hospitalizations, including elective hospitalizations for any condition that was not pre-existing, will be reported as a SAE.

All SAEs, whether or not considered related to study treatment, must be reported to the sponsor Contact within 24 hours of becoming aware of the event. In addition, a completed report using the sponsor's SAE form must be submitted within 24 hours of notification to:

Arena Drug Safety and Pharmacovigilance Arena Pharmaceuticals, Inc. [name]

Other situations as defined in ICH Topic E2A, 21 CFR§ 312.32, and EU Volume 10 also qualify for expedited reporting. In these situations the process will be as detailed for SAEs above:

- Serious adverse events which could be associated with the trial procedures;
- Serious adverse events and adverse events of special interest that could materially influence the benefit-risk assessment of a medicinal product, such as: a clinically important increase in the rate of a serious suspected adverse reaction over that listed in the investigator brochure.

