- 6MWTs 2 consecutive tests done on different days
- Thromboembolic disease assessment to include a ventilation-perfusion lung scan (VQ Scan) or spiral/helical/electron beam computed tomography utilizing an

angiography protocol, or selective pulmonary angiogram, unless performed within 5 years prior to Screening

- Pulmonary function testing including measurement of total lung capacity (TLC), unless performed within 6 months prior to Screening
- Transthoracic or transesophogeal ECHO unless performed within 12 months prior to Screening
- Right heart catheterization performed within 1 month prior to Day 1 Patients who have had a RHC performed within 30 days of screening and who meet study entry requirements are not required to have a repeat screening RHC
- Record concomitant medications
- Record adverse events

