#### 7.3.1.1 Pre Day 1 Procedure

RHC measurements for baseline measurement will be performed within **30 days** of screening. Any AE related to study procedures will be recorded. A RHC measurement will be performed as part of end of study assessments.

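### SAP 5.3 records every adverse event between screening and first dose as medical history, which conflicts with the protocol and is not declared as a change

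*SAP*

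**What the plan says.** SAP 5.3 defines pre-treatment AEs as those between screening and "the time of administration of the first dose of APD811 or placebo and will be recorded as medical history". Events that start or worsen after the first dose are treatment-emergent (TEAEs). The SAP's AE listing and its incidence tables are for TEAEs, and the SAE summary is one of the tables counting patients with at least one TEAE. A separate sentence provides an SAE listing and does not limit it to treatment-emergent events.

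The protocol handles the same period differently:

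- Section 6.13.1 calls events pre-treatment "if they occur between Screening and the time of administration of the first dose of APD811" and goes no further. Sections 8.2.1 and 9.5.3.2 repeat the label. None of them moves the events to medical history.
- Section 7.1 includes "Record adverse events" among the screening activities.
- Section 7.3.1.1, on the baseline RHC, states "Any AE related to study procedures will be recorded".
- Section 6.13.2 states "SAEs will be captured from the time of screening to 30 days after the dose of study drug", and its list for expedited reporting includes "Serious adverse events which could be associated with the trial procedures".

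The footnote to Protocol Table 1 states "A Baseline RHC is required". It adds that eligible patients with an RHC within 30 days of screening "are not required to have a repeat screening RHC".

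**The concern.** The screening period lasts up to 28 days and, for patients without a recent eligible RHC, includes an invasive procedure done for the trial. A complication of that procedure is a harm of taking part. Recorded as medical history, it would read as a condition the patient brought into the trial.

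The study report would then have no defined AE output for harms of the screening procedures. An SAE already reported to the sponsor under Protocol 6.13.2 might have no clear counterpart in the analysis outputs. SAP 5.3 also says that if there are no SAEs at the end of the study, the tables or listings will say so. If the only SAE were a screening complication filed as medical history, that statement could be wrong.

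**Working it through.** The plan gives no figure to reproduce here. The check compares the rules for a pre-dose event.

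| Question | Protocol | SAP |
|---|---|---|
| What is it called? | Pre-treatment AE (6.13.1, 8.2.1, 9.5.3.2) | Pre-treatment AE, recorded as medical history (5.3) |
| Is it collected as an AE? | Yes, at screening (7.1) and for study procedures (7.3.1.1) | Filed as medical history (5.3) |
| Is a serious one captured as an SAE? | Yes, from screening (6.13.2) | No exception for serious events (5.3) |
| Is it in the AE listing and tables? | No, post-dose events only (9.5.3.2) | No, TEAEs only (5.3) |
| Is it in the SAE summary? | No separate SAE summary described | No, the summary counts TEAEs (5.3) |
| Is it in the SAE listing? | No separate SAE listing described | Unclear: the listing is not limited to TEAEs, but the event has been reclassified (5.3) |
| Is it shown elsewhere? | Medical history listed, abnormalities only (9.5.3.1) | Medical history listed, abnormalities only (2) |

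**Step 1: the conflict.** The first three rows differ. The SAP takes a step that the protocol does not. SAP section 9 lists the changes from the protocol and does not name this one. Only its general reference to clarified data handling could cover it, and turning an AE into medical history is more than a clarification.

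**Step 2: what is lost.** Protocol 6.13.1 and 6.13.3 give an AE a severity grade, onset, duration, outcome and relationship to drug. SAP section 2 states none of these for medical history, nor seriousness.

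**Step 3: side effects within the SAP.** The TEAE definition includes worsening after first dose. Detecting worsening needs a pre-dose severity, which the medical-history listing is not said to carry. The AE start-date rules in SAP 7.4 can also place an incomplete date before first treatment, so AE records with pre-dose onset are expected to exist.

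**Step 4: which procedures are affected.** Only those before first dose. The Week 22 RHC falls after first dose, so its harms remain treatment-emergent.

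**Step 5: scale.** The documents give no rate of screening-procedure events, so the rates below are assumptions. With per-patient rate p and 60 randomised patients, the expected number is 60 × p and the chance of at least one is 1 − (1 − p)^60.

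| Assumed p | Expected events | Chance of at least one |
|---|---|---|
| 0.5% | 0.3 | 1 − 0.995^60 = 26% |
| 1% | 0.6 | 1 − 0.99^60 = 45% |
| 2% | 1.2 | 1 − 0.98^60 = 70% |
| 5% | 3.0 | 1 − 0.95^60 = 95% |

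This takes all 60 as having the RHC within the trial. The 30-day exemption lowers these figures. Patients who had the procedure and were never randomised are not counted.

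**The case against.** A reader might infer that harms of the trial's procedures vanish from the AE and SAE outputs altogether. The documents do not support that, for these reasons, all of which stand:

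- **SAE listing.** Its sentence in SAP 5.3 has no treatment-emergent restriction. A pre-dose SAE is not excluded; its inclusion is ambiguous.
- **Still visible.** Medical history is listed for all patients, and an event that worsens after first dose is still a TEAE.
- **Reporting duties.** The 24-hour SAE reporting and the expedited reporting in Protocol 6.13.2 are not changed by the SAP.
- **Procedures covered.** Week 22 RHC harms stay in the TEAE outputs, and the screening RHC is not universal because of the 30-day exemption.
- **The protocol's own plan.** Protocol 9.5.3.2 already limits AE listings and summaries to post-dose events, so the missing pre-treatment output did not begin with the SAP. The protocol's AE definition (6.13.1), which refers to a patient given study medication, also fits poorly with its own pre-treatment label.

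Two practical points also stand. Protocol 6.13.4 assesses relationship to investigational product only, and no field for relationship to a procedure is described. The safety population in SAP 5.1 consists of randomised, dosed patients, so someone harmed at screening and never dosed is outside it. The fix has to allow for both.

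These points narrow the consequence. They do not remove the conflict over classification, the missing entry in SAP section 9, or the doubt about the SAE listing.

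**Conclusion.** The point holds in a limited form. SAP 5.3 reclassifies all pre-dose AEs as medical history, serious and procedure-related ones included, against the protocol and without declaring it. Pre-dose AEs that do not worsen on treatment would lose AE-style severity, seriousness and relationship. Pre-dose SAEs are outside the SAE summary, and their place in the SAE listing is undecided.

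The effect is on harms reporting for a screening period of up to 28 days. The efficacy analyses and the type I error rate are untouched. The between-arm TEAE comparison is essentially unaffected because these events precede treatment; the one qualification is the pre-dose severity needed to judge worsening. How many events are involved cannot be known from the documents, and the chances in the working rest on assumed rates. The rule should still be corrected, because a single serious screening complication would be enough to make the outputs misleading and the correction is small.

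**What to change.** 1. In SAP 5.3, delete the clause that assigns pre-treatment AEs to medical history.
2. Keep these events in the AE data with a pre-treatment flag.
3. State that the SAE listing starts at screening, in line with Protocol 6.13.2.
4. Add one listing of pre-treatment AEs and SAEs. It should cover all patients with such events, including those never dosed, and show relationship to a study procedure where the investigator recorded it.
5. Leave the TEAE tables unchanged.

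The cost is a small SAP edit and one extra listing. Showing procedure relationship only where it was recorded avoids a new data-collection field, so that column may be incomplete.
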